Population and patient selection criteria

A cohort of 100 adults (18-75 years) patients with UC, either naïve or under standard of care (both responders and non-responders to therapies) will be prospectively enrolled. In all cases, the Montreal classification, and the clinical and endoscopic indexes of activity will be carefully assessed. The control group consists of 100 sex- and age-matched subjects, selected in the same Center, undergoing colonoscopy as examination in the diagnostic algorithm for lower abdominal symptoms and **that results normal, thus confirming the diagnosis of** irritable bowel syndrome, and who were not taking drugs possibly affecting immune response and microbiota composition. **A small cohort of patients (n=20) suffering from microscopic colitis will be also enrolled as pathological control group.** All enrolled patients and controls will undergo lower endoscopy with mucosal sampling as **diagnostic** workup for their condition. Patients with active UC undergo colonoscopy and laboratory tests according to international

guidelines and depending on physician judgement. More in depth, active UC patients will undergo colonoscopy at baseline, while laboratory tests will be performed at baseline, and at 3 and 6 months. As optional follow-up, accordingly with physician evaluation, some patients will undergo medical examination and laboratory tests at 9 and 12 months, and colonoscopy at 12 months. The aim of the study is settled at 6 months, but adding the optional follow-up at 9 and 12 months, will aid us to understand if patients with EBV colitis undergo colectomy more frequently than patients without EBV colitis. Patients with UC in remission will undergo colonoscopy and laboratory tests according to ECCO-ESGAR guidelines [52]. Patients with suspicion of irritable bowel syndrome will undergo colonoscopy and laboratory tests if alarm features are present (aged >45-50 years, anemia, weight loss, familiar history of colon cancer, blood mixed in the stool). The exclusion criteria include: significant comorbidities, malignancy, pregnancy, organ failure, immunodeficiencies, active infections, recent abdominal surgery, or invalidating psychiatric-neurological disorders.

The sample size has been calculated based on the primary endpoint, i.e., the prevalence of EBV infection in UC patients. The power to detect a significant difference with the Fisher exact test from an expected proportion in controls of 1% is above 80% for proportions of infection of 20% or greater.

This is an investigator-initiated prospective multicentre interventional without drug and medical device study evaluating the prevalence, role, life phase and the most accurate diagnostic method of EBV infection in UC as assessed by means of traditional method (*in situ* hybridization) and quantitative RealTime-PCR assay. A longitudinal study is included to assess whether EBV infection has an impact on patients' outcome. The study duration is three years.

**Study design and study
duration**

Objectives and end-points

The primary objective consists of the evaluation of the prevalence of EBV infection, defined as isolation of the EBV or detection of viral proteins or nucleic acids in any body fluid or tissue specimens.-in patients suffering from UC. The same analyses will be performed in a comparable cohort of non-IBD patients who undergo lower endoscopy during their work-up for irritable bowel syndrome (IBS) and microscopic colitis. ~~(new diagnosis, responders, non-responders) in order to unravel whether it is a bystander or causative of the onset/relapse of the disease and whether it is responsible for refractoriness to standard of care.~~ The secondary objectives include: a) comparison of the presence of EBV infection in the cohort of patients suffering from UC and divided into the following subgroups: new diagnosis, responders, non-responders, in order to unravel whether it is a bystander or causative of the onset/relapse of the disease and whether it is responsible for refractoriness to standard of care; b) evaluation of the diagnostic ability in detection of EBV infection of ISH performed on mucosal specimens with respect to qRealTime-PCR; ~~of *in situ* hybridization with respect to quantitative RealTime-PCR;~~ c) evaluation of diagnostic ability in detection of EBV infection between qRealTime-PCR performed on peripheral blood samples with respect to mucosal specimens; ~~association between viral load and clinical and endoscopic indexes of activity~~ c) evaluation of association between therapeutic agents and EBV infection; d) evaluation of association between mucosal/blood viral load and mucosal damage as endoscopically assessed; e) evaluation of association between clinical index of UC activity and EBV infection; f) evaluation of association between steroid therapy (absent, previous or current) and EBV infection; g) evaluation of association between immunosuppressive therapy (absent, previous or current) and EBV infection; h) evaluation of association between biological therapy (absent, previous or current) and EBV infection; i) evaluation of the prognostic role of EBV infection on the 6 and 12 month outcome (colectomy / number of hospitalization / cause of

hospitalization). The exploratory endpoints include the study of the virus life cycle phase and its correlation with disease activity.

**Statistical methods, data
analysis**

Data will be described with the mean and standard deviation or the median and 25th-75th percentiles if continuous and as counts and percent if categorical. For the primary endpoint we will compute the prevalence as the ratio of the number of patients diagnosed with EBV infection to the number of patients evaluated, together with its 95%CI. We will use the Fisher exact test to compare the prevalence in UC patients to that of control. We will use binomial regression models to adjust for potential confounders. We will compute sensitivity, specificity, area under the ROC curve and predictive values with 95%CIs. We will use the Spearman R and the Fisher exact test to assess the association, for continuous and categorical independent variables, respectively, with dependent variables. We will use Cox regression to assess the association of EBV infection with colectomy and of hospitalization for any cause; we will use Poisson regression to assess the association of EBV infection with the number of hospitalization from any cause. We will use Stata 17 or later versions for computations. A 2-sided p-value <0.05 will be considered statistically significant. We will apply the Bonferroni correction for post-hoc comparisons.

Ethical considerations

The protocol and its annexes are subject to review and approval by the competent Independent Ethics Committee(s). Each patient and control gives written informed consent after approval by the local Ethics Committee is obtained. Both the Principal Investigators and the Study Coordinator will ensure that this study is conducted in agreement with either the Declaration of Helsinki and the Italian laws and regulations.

Study time table

[figure not shown]
Project starting date: 30.10.2022

Project completion of data collection: 30.05.2025

Project data analysis: 31.07.2025

Project presentation of scientific report: 30.10.2025

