5.2.2 Secondary endpoint

a- Comparison of the presence of EBV infection in the cohort of patients suffering from UC and divided into the following subgroups: a) new diagnosis; b) responders to conventional therapies; c) non-responders to conventional therapies, in order to unravel whether it is a bystander or causative of the onset/relapse of the disease and whether it is responsible for refractoriness to standard of care.

b- Evaluation of the diagnostic ability in detection of EBV infection of ISH performed on mucosal specimens with respect to qRealTime-PCR.

c- Evaluation of the diagnostic ability in detection of EBV infection between qRealTime-PCR performed on peripheral blood samples with respect to mucosal specimens.

d- Evaluation of association between mucosal/blood viral load and mucosal damage as endoscopically assessed (see paragraph 5).

e- Evaluation of association between clinical index of UC activity and EBV infection.

f- Evaluation of association between steroid therapy (absent, previous or current) and EBV infection.

g- Evaluation of association between immunosuppressive therapy (absent, previous or current) and EBV infection.

h- Evaluation of association between biological therapy (absent, previous or current) and EBV infection.

i- Evaluation of the prognostic role of EBV infection on the 6 and 12 months outcome (colectomy / number of hospitalization / cause of hospitalization).

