8.2 Analysis

Data will be described with the mean and standard deviation or the median and 25th-75th percentiles if continuous and as counts and percent if categorical. For the primary endpoint we will compute the prevalence as the ratio of the number of patients diagnosed with EBV infection to the number of patients evaluated, together with its 95%CI. We will use the Fisher exact test to compare the prevalence in UC patients to that of control. We will report the mean difference in proportions and its 95%CI. We will use binomial regression models with identity link (command binreg in Stata), to adjust for potential confounders, such as, but not limited to, age, gender, duration of disease and treatment. We will apply the 1:10 rule to adapt the number of confounders evaluated to the sample size. We will compare the prevalence of EBV infection between UC subgroups with the Fisher exact test (EP2a). In these cases, given in particular that the ratio of responders to non-responders is at yet unknown, we will compute *a posteriori* the power for the comparison. We will compute

sensitivity, specificity, area under the ROC curve and predictive values with 95% CIs for EP2b and EP2c. We will use the Spearman R and the Fisher exact test to assess the association, for continuous and categorical independent variables, respectively, with the dependent variables of EP2d to EP2h. All estimates will be presented with their 95% CI.

We will use Cox regression to assess the association of EBV infection with colectomy and of hospitalization for any cause; we will use Poisson regression to assess the association of EBV infection with the number of hospitalization from any cause. For secondary endpoints assessing associations, we will also fit regression models to adjust for possible confounders (as for the EP1) and report adjusted mean differences in proportions and 95% CI. We may also use propensity score inverse probability weights to account for the bias by indication when assessing treatment effect on the outcome.

The exploratory endpoints will be only descriptive.

We will use Stata 17 or later versions for computations. A 2-sided p-value <0.05 will be considered statistically significant. We will apply the Bonferroni correction for post-hoc comparisons.

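### Bonferroni for post-hoc pairs costs power in the three-group secondary comparisons (EP2a, EP2f to EP2h), where closed testing holds the same within-factor 5%

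*Protocol*

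**What the plan says.** The Summary (statistical methods) and Section 8.2 carry the same rule: "We will apply the Bonferroni correction for post-hoc comparisons". Section 8.2 also sets the threshold: "A 2-sided p-value <0.05 will be considered statistically significant". Neither place lists the post-hoc comparisons or defines the family over which the correction runs.

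Section 5.2.2 defines four secondary endpoints with exactly three groups:

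- EP2a: "a) new diagnosis; b) responders to conventional therapies; c) non-responders to conventional therapies"
- EP2f: "Evaluation of association between steroid therapy (absent, previous or current) and EBV infection"
- EP2g: "Evaluation of association between immunosuppressive therapy (absent, previous or current) and EBV infection"
- EP2h: "Evaluation of association between biological therapy (absent, previous or current) and EBV infection"

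Section 8.2 assigns the Fisher exact test to EP2a and to categorical factors in EP2d to EP2h. Section 8.1 plans about 100 UC patients and expects an EBV prevalence of about 50% in non-responders and 10% in responders. It gives no rate for new diagnoses. Section 8.2 says that the ratio of responders to non-responders is not yet known.

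**The concern.** On the natural reading, an overall three-group test is followed by three pairwise tests, each at 0.05/3. For three groups that is stricter than a 5% familywise guarantee requires. EP2a is the comparison meant to show whether EBV is linked to disease onset or to refractoriness. It divides about 100 patients, a number set by feasibility, over three subgroups. Power for moderate differences is then low, and the stated correction lowers it further although another procedure gives the same 5% guarantee within the factor.

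**Working it through.** **Check of the method.** Enumerating every outcome of a two-sided Fisher exact test with 100 against 100, alpha 0.05 and 1% in controls gives power of 76.9%, 99.8%, 100% and 100% at UC prevalences of 10%, 20%, 30% and 50%. These are the figures in the Section 8.1 table, so the enumeration matches the protocol's own calculation.

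**Why three groups are special.** Call the pairwise null hypotheses H12, H13 and H23. If any two are true, all three groups are equal and the third is true as well. The only intersection hypothesis is therefore the global null H123. By the closure principle, Hij may be rejected when both H123 and Hij are rejected at 0.05, and the familywise error within the factor is at most 5%.

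**Inputs.** From the protocol: alpha 0.05 two-sided, about 100 UC patients, 10% in responders, 50% in non-responders, Fisher tests. Assumed, because the protocol does not give them: the split and the rate in new diagnoses. The splits, as new/responders/non-responders, are 20/40/40, 34/33/33 and 30/50/20.

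**Rules compared**, over all outcomes of three independent binomial groups:

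- Bonferroni: pairwise Fisher p ≤ 0.05/3.
- Closed: three-group Fisher (Freeman-Halton) p ≤ 0.05 and pairwise Fisher p ≤ 0.05.

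**Familywise error.** Prevalences were scanned from 5% to 95%, with all three groups equal and with each pair equal. The maximum was 4.8% for closed testing in each split, and 3.1 to 3.3% for Bonferroni.

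**Power, Bonferroni to closed (%), with 30% / 10% / 50%** (gains taken before rounding):

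| Split | Responders vs non-responders | New vs responders | New vs non-responders |
|---|---|---|---|
| 20/40/40 | 93.4 to 96.6 (+3.2) | 29.9 to 43.7 (+13.8) | 14.4 to 24.6 (+10.1) |
| 34/33/33 | 85.8 to 91.8 (+6.1) | 27.5 to 45.2 (+17.7) | 21.1 to 35.7 (+14.6) |
| 30/50/20 | 85.0 to 90.9 (+5.9) | 44.1 to 56.4 (+12.2) | 13.8 to 26.0 (+12.2) |

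The gain for responders versus non-responders depends slightly on the new-diagnosis rate, because that rate affects the overall test. With 10%, 30% or 50% in new diagnoses it runs from 3.2 to 7.8 points over the three splits.

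If non-responders are at 30% and both other groups at 10%, the 20/40/40 split gives 34.5 to 49.5 for responders versus non-responders and 17.5 to 33.9 for new versus non-responders.

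**Does the overall test block anything?** In these three splits there was no outcome in which a pair was significant under Bonferroni while the overall test was not.

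**Wider assumptions.** Over ten splits, with new-diagnosis rates from 10% to 50%, the gain on truly different pairs runs from about 1 to 21 points. For responders versus non-responders it is about 1.5 to 9 points.

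**EP2f to EP2h.** The protocol gives neither rates nor group sizes, so no power was computed. The error argument applies because each has three levels.

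**The case against.** **Nothing is stated wrongly.** This stands. Bonferroni holds 5%, the endpoints are secondary, and the primary UC-versus-control test is untouched. A reader might infer that the plan's error control is faulty; it is not.

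**The target of the rule is undefined.** This stands too. A reader might infer that the protocol expressly imposes 0.0167 on EP2a and EP2f to EP2h. It does not. Section 8.2 plans the EP2a comparison in advance and mentions no correction beside it. If post-hoc means unplanned comparisons only, the loss on EP2a disappears.

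**The large gains rest on assumed rates.** This is correct. A reader might take up to 18 points as the gain on the main contrast. For responders versus non-responders, the one contrast with both rates in the protocol, it is about 3 to 8 points in the three splits.

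**Bonferroni protects somewhat more.** A reader might infer that the two rules protect equally. They share the 5% bound, but the attained maxima differ (3.1 to 3.3% against 4.8%). Neither rule, applied factor by factor, holds 5% over four factors. Treating the factors as independent, 1 − (1 − 0.048)^4 = 17.9% for closed testing and 1 − (1 − 0.033)^4 = 12.6% for Bonferroni. The protocol defines no family across factors, so this is a cost to state and not a reason to reject the change.

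**Intervals.** Section 8.2 wants all estimates with 95% confidence intervals. Bonferroni extends directly to simultaneous intervals that match its tests; closed testing and Holm have no such simple match. This stands as a cost.

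**Coverage.** A replacement limited to EP2a and EP2f to EP2h would leave pairwise tests among UC, IBS controls and microscopic colitis, and contrasts from the adjusted regression models, without a rule. The fix has to cover them.

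**Conclusion.** The point holds as a cheap gain in efficiency on secondary endpoints. On the reading that post-hoc comparisons are the pairwise tests within three-group factors, closed testing keeps the within-factor familywise error at 5%. In the splits examined it rejected every pair that Bonferroni rejected.

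The gain is about 3 to 8 points for responders versus non-responders at 10% and 50%, and about 10 to 18 points for contrasts with an assumed 30% rate. These figures rest on the three assumed splits, the assumed new-diagnosis rate and the undefined term. They do not show an error in the plan or any effect on the primary analysis.

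**What to change.** Replace the Bonferroni sentence in Section 8.2 and the Summary, before any results are seen, with:

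> For three-group comparisons, pairwise Fisher tests are done only if the overall three-group Fisher test has p<0.05, and each is then tested at 0.05 (closed testing, controlling the familywise error within each factor). Holm's procedure is used for all other post-hoc comparisons, including contrasts from regression models.

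The sentence concerns post-hoc comparisons only; the primary UC-versus-control Fisher test stays as it is. Holm rejects everything that Bonferroni rejects, at the same error rate, so nothing is lost outside the three-group case.

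The change needs no patients or data. It has three costs, which the plan should state:

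- No pair can be claimed unless the overall test is significant.
- The reported 95% confidence intervals are not simultaneous intervals matching the tests.
- Error is controlled within each factor, not across the four.

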2 STUDY FLOW CHART FOR ACTIVE ULCERATIVE COLITIS PATIENTS

3 BACKGROUND AND INTRODUCTION

- ❖ Inflammatory bowel disease (IBD), namely Crohn's disease and ulcerative colitis (UC), are emerging chronic and disabling enteropathies triggered and sustained by a dysregulated immune response towards antigens of the gut microbiota in genetically susceptible individuals (1,2). The growing use of immunosuppressive therapies, mainly based on biological agents, to achieve mucosal healing and prevent disease progression (3), has led to an increased risk of opportunistic infections (4,5,6), including that caused by the Epstein-Barr virus (EBV) (7). In this regard, although a considerable number of studies support the notion that colonic involvement through opportunistic viral infection in existing IBD is associated with a worsening of symptoms, increased prevalence of refractoriness and surgical intervention [8,9,10,11], the role played by EBV in UC, whether contributor or innocent bystander, remains a topic of ongoing controversy [12,13]. EBV infection is usually acquired early in the life and is generally asymptomatic in healthy people where it establishes a lifelong latency in target cells (memory B-cells) (14), while it reactivates in case of reduced host immunity (15). EBV, indeed, exists in two possible states of its life cycle, latent and lytic (16,17,18). The latter usually occurs in immunocompromised hosts where it eventually results in systemic or end-organ diseases leading to increased morbidity and mortality (19). Localizing in the gastrointestinal tract (20,21) represents a clinical challenge in IBD since it becomes hard to distinguish between a superimposed viral colitis and a relapse of the underlying disease. In this regard, the ECCO guidelines state that: "*Screening for EBV infection (through the search of specific anti-virus immunoglobulin) before initiation of immunomodulator therapy should be considered. In severe primary clinical EBV infection during immunomodulator therapy, antiviral therapy may be considered and immunomodulator therapy discontinued. In the event of EBV-driven lymphoproliferative disease during immunomodulator therapy, the patient should be managed in conjunction with appropriate specialists. Immunomodulators should be stopped*" (22). It appears clear that the main focus is lymphoma-driven (23), with almost no mention of secondary symptomatic infection due to reactivation of the lytic phase of the virus life cycle, that is the most frequent condition in clinical practice. As a consequence, several crucial points still remain unsolved, such as its true prevalence and role in tissue damage, the best diagnostic and therapeutic approach, as well as the identification of risk factors still remains elusive.
- ❖ This is why a number of important issues related to EBV infection in the specific clinical setting of IBD, namely its life cycle, its interaction with the host immune system, and virus–

cell interaction has received little or no attention. Interestingly, the clinical features of UC, such as the pick of onset at young age, the association with a life-stressing event, the unpredictable clinical course, and even the evolution towards toxic megacolon, all fit with EBV infection. Moreover, our previous demonstration of the presence of EBV DNA in epithelial cells of those samples harvested from diseased UC mucosa but not from healthy mucosa of non-IBD controls (24) gives an explanation of the contiguity of lesions, that is a hallmark of this condition. Indeed, it is known that EBV uses epithelial cells for its lytic cycle and to spread locally in tissues and, possibly, systemically (17,25). It is conceivable, therefore, that in the event of switch of virus infection from latency to lytic phase, the ability to infect neighboring epithelial cells (26,27) is responsible for the extension of its localization to more proximal tracts. Moreover, the loss of the ability of the host immune system to circumvent this switch due to malnourishment and/or therapies (28) whose main target are T-cells which play a crucial role in controlling EBV latency and reactivation (18), represents a potential trigger for a superimposed viral colitis. Also a key event in the life of a person may largely affect the mutual relationship between the virus and the host, giving rise to the onset the disease and/or of its flare-up (29).

- ❖ Therefore, we aim to prospectively evaluate the presence of EBV infection with the analysis of its cycle phase (latent or lytic) in a cohort of UC patients, in order to investigate its contribution to disease onset, activity and relapse, together with the analysis of possible risk factors of its activation. Finally, shall we find the capability of EBV to establish latency (30) even in epithelial cells, the possibility of its contribution in the development of dysplasia/carcinoma sequence in inflamed mucosa becomes a valid hypothesis (31).
- ❖ To date, the information available on the frequency, role and risk factors of EBV infection/disease in UC as well as its diagnostic and therapeutic approach is conflicting (7,10,12,20,21). The causes for this discrepancy lie in the differences amongst the patients enrolled, the diagnostic methods applied, and the retrospective design of the majority of studies. Therefore, no firm conclusion may be drawn on the real incidence and role of EBV infection in UC. Surely, an increased risk of lymphoma has been found in IBD patients under immunosuppressive therapy, especially among young males under thiopurines, where a role for primary EBV infection has been proposed (23,32) as in the case of post-transplant lymphoproliferative disease (33). Following the ECCO guidelines for the diagnosis and treatment of opportunistic infections, where only a short paragraph is reserved to EBV (22), the diagnosis of primary infection should be based on the evidence of the detection of class M and G immunoglobulin against the EBV viral capsid antigen (VCA) with negative EBNA1

IgG, whereas no mention of reactivation of latent infection is given. Moreover, it is stated that viral load measurement (without specify whether in the blood or at mucosal level) after establishment of an immunomodulatory therapy has negligible relevance without an EBV-associated disease (without specify whether systemic or an end-organ disease, like colitis). It appears clear that the issues regarding the management of EBV infection in IBD are extrapolated from the haematologic conditions, since no robust experience in this gastroenterologic setting is available. At this point, it should be underpinned that the definitions of EBV infection and colitis have been often used interchangeably, thus creating further confusion. Moreover, no recommendations are given about the therapeutic management of a superimposed EBV colitis in UC and, on the other side, no valid treatments are available for EBV infection itself. Finally, as far as the outcome is concerned, a clear association between EBV infection and a poor prognosis, mainly in terms of an increased incidence of colectomy, appears evident from the literature (34).

- ❖ Our previous studies have clearly showed the need for quantitative real time polymerase chain reaction (qRealTime-PCR) analysis performed on mucosal samples not only for its better diagnostic accuracy in comparison to *in situ* hybridization (ISH) and immunohistochemistry, but mostly in order to stratify the patients, since a positive result does not necessarily imply that the patient is suffering from an EBV-related end-organ disease (35). Indeed, we identified a cutoff of 1000 copies/100.000 cells as the value to distinguish a superimposed viral colitis from a pure relapse of the underlying disease (35). Furthermore, since no efficacious therapy is currently available for symptomatic EBV infection, the only possible intervention consists of a quick tapering and then discontinuation of steroids, while improving malnutrition if present. By contrast, the immunosuppressive and biological agents could be continued by virtue of their long-lasting effects. We also suggested a note of caution in prescribing steroids and biologics in those patients carrying a mucosal viral load of between 100 and 1000 copies, who should be closely monitored, while no modification of the standard treatment is needed for those with a mucosal viral load lower than 100 copies (36). In this regard, it should be emphasized that the search for circulating class M specific anti-virus antibodies is rather ineffective in detecting an active disease, since elevated levels can persist for up to two years after infection, while immunocompromised patients may not mount an IgM response (37).
- ❖ In addition, our evidence of localization of virus infection in colocytes represents the first step towards understanding the mechanisms of viral dissemination and the role of the lytic phase in tissue damage (24). Indeed, a suggested viral tropism to sites of inflammation, and its

ability to affect cytokine production (20) may account for how it escapes host immune surveillance directly at mucosal level. Here, resting memory B cells serve as the long-term reservoir of latent EBV infection, and their differentiation into plasma cells in response to inflammatory stimuli may trigger the lytic phase and subsequent release of viral particles (38), leading to viral replication (15,16,17). Moreover, T-cell action in controlling viral replication (18) may be hampered by concurrent malnourishment and immunosuppressive drugs, thus resulting in an uncontrolled activation of the lytic phase of the viral life cycle which localizes precisely in the target organ (21).

- ❖ Therefore, we aim to carry out a multicenter interventional without drug and medical device study in order to definitely prove whether EBV infection represents a causative factor in tissue damage or a surrogate marker of severe colitis (13), an issue that may greatly contribute to understanding the mutual relationship between the host and the virus and to correctly manage the patients. The parallel analysis of the Human Cytomegalovirus (HCMV) load will assure a better understanding of the role of EBV. The possibility to involve the IG-IBD Centers gives the assurance for the study feasibility. Furthermore, the presence of clinicians with high expertise on histologic examination of IBD samples (Doctor [name]) and opportunistic viral infections ([name]) gives more strength to the proposal. We thus intend to recruit patients suffering from UC, either naïve to therapy or under treatment (both responders and non-responders) and non-IBD controls in order to evaluate the real prevalence, role and risk factors of EBV infection in this peculiar clinical setting. Moreover, by using qRealTime-PCR and ISH in parallel, we want to definitely establish the better diagnostic tool. Finally, the duration of three years seems the right length of the study to recruit a sizable number of patients and evaluate their outcome, as well as to perform the analysis and interpretation of results.

